ABR	ABR form, General Assessment and Registration form, is the application form that is required for submission to the accredited Ethics Committee (In Dutch, ABR = Algemene Beoordeling en Registratie)
AE	Adverse Event
AR	Adverse Reaction
CA	Competent Authority
CAT	COPD Assessment Test
CCMO	Central Committee on Research Involving Human Subjects; in Dutch: Centrale Commissie Mensgebonden Onderzoek
CV	Curriculum Vitae
COPD	Chronic Obstructive Pulmonary Disease
DSMB	Data Safety Monitoring Board
EU	European Union
EudraCT	European drug regulatory affairs Clinical Trials
FNA	Formularium Nederlandse Apothekers
GCP	Good Clinical Practice
IB	Investigator's Brochure
IC	Informed Consent
IMP	Investigational Medicinal Product
IMPD	Investigational Medicinal Product Dossier
METC	Medical research ethics committee (MREC); in Dutch: medisch ethische toetsing commissie (METC)
NRS	Numeric Rating Scale
(S)AE	(Serious) Adverse Event
SPC	Summary of Product Characteristics (in Dutch: officiële productinformatie IB1-tekst)
Sponsor	The sponsor is the party that commissions the organisation or performance of the research, for example a pharmaceutical company, academic hospital, scientific organisation or investigator. A party that provides funding for a study but does not commission it is not regarded as the sponsor, but referred to as a subsidising party.

SUSAR	Suspected Unexpected Serious Adverse Reaction
Wbp	Personal Data Protection Act (in Dutch: Wet Bescherming Persoonsgegevens)
WMO	Medical Research Involving Human Subjects Act (in Dutch: Wet Medisch-wetenschappelijk Onderzoek met Mensen)

SUMMARY**Rationale:**

Xerostomia, the subjective feeling of dry mouth, is a frequent symptom in the elderly. Xerostomia leads to functional alterations and has disabling social consequences and reduces quality of life.

Objectives

The objective of this study is to deliver the “proof-of-concept” that locally administered pilocarpine drops are effective in a population of elderly with xerostomia at expense of a minimum of side effects.

Study design:

Open-label randomised controlled pilot study

Study population:

Patients of advanced age (≥ 70 years) with a clinical diagnosis of chronic dry mouth (NRS score of ≥ 5) visiting the outpatient clinic of MUMC+.

Intervention:

Local administration of pilocarpine (eye)drops orally in a low dose or a high dose for 14 days.

Main study parameters/endpoints:

Change in xerostomia score

Change in oral health-related quality of life

Secondary study parameters/endpoints

- Adverse effects
- Other symptoms
- Global perceived effect

Nature and extent of the burden and risks associated with participation, benefit and group relatedness:

The extent of the burden associated with participation in this study is considered to be low. Total follow up will last a total of 3 weeks. In these 3 weeks the patient will visit the hospital twice and will be contacted through phone calls twice. Local oral administration of pilocarpine is reported to have none or only minor side effects. During the two hospital visits whole resting saliva will be collected, and blood pressure will be measured. The burden of both these procedures is considered low. The patient will also be asked to complete a total of four questionnaires in these 3 weeks. These questionnaires consists of 45 questions, which will take 20 minutes, the level of burden is low.

1. INTRODUCTION AND RATIONALE

Introduction

Xerostomia is the subjective feeling of dry mouth, a symptom associated with alterations in the quality and quantity of saliva. Xerostomia leads to functional alterations such as halitosis, burning sensations, altered taste perception, pain, and difficulties of chewing, swallowing, speaking and sleeping.[1, 2] Also, xerostomia has disabling social consequences[3] and reduces quality of life.[2, 4-8]

Xerostomia has been associated with radiation therapy, the use of medications, various chronic diseases and/or poor health.[2] Reported prevalence rates among patients with cancer, Chronic Obstructive Pulmonary Disease (COPD) or heart failure are about 50%.[9-11] The prevalence among community-dwelling elderly ranges from 17% to 40%.[2] In a cohort of vulnerable elderly the prevalence of xerostomia was estimated at 100%, with low, moderate, and high xerostomia according to the xerostomia index at a rate of 49.3%, 30.3%, and 20.4%, respectively.[8]

In the elderly, xerostomia is mostly caused by side effects of chronic drug treatment in combination with a 30%-40% decrease of acinar cells of salivary glands between the ages of 34 and 75 years.[1]

Withdrawal or substitution of xerostomia-inducing drugs is the most effective treatment. However, this does not always outweighs the drug's benefits, e.g. with treatment of depression or pain.

Therefore other treatment possibilities to effectively reduce xerostomia and improve quality of life should be considered.

Current symptomatic treatment options include local treatment with artificial saliva/mouthwashes or systemic or local administration of pilocarpine. The former has mainly been researched in advanced cancer patients[12, 13] and was not better than chewing gum.[14] The latter are the current mainstay treatment of patients in the palliative phase of their illness.[12] Pilocarpine is a parasympathomimetic drug that increases saliva production by activating muscarinic receptors.[12] Pilocarpine tablets (systemic treatment) are more effective than placebo in radiation-induced xerostomia,[15-18] Sjögrens disease, [19] tramadol induced oral dryness[20] and improved salivation in patients taking xerogenic medications.[21] However, systemic administration of pilocarpine has frequent side-effects such as sweating (20 -50%), flushing, rhinitis (12%), headaches (12%), increased frequency of urination (11-34%), flu-like symptoms (8%), asthenia (7%)[21-23] and, mainly in elderly patients, dizziness (17%) leading to dropout rates between 6% and 15% in clinical studies.[16] Local oral administration of pilocarpine (drops, lozenges and mouthwashes) are reported to have none [24, 25] or minor local side effects (irritation of mouth and tongue).[26] In addition, a 5 mg pilocarpine lozenge produced better clinical results than a 5 mg pilocarpine tablet in 33 head-and-neck cancer

patients.[27], Furthermore, pilocarpine eye drops 2% relieved xerostomia immediately in 19 patients with opioid-induced complaints of dry mouth.[25] However, inconclusive results have been reported about the effectiveness of these local formulations in other studies.[24, 28].

Literature is scarce on the effectiveness of pilocarpine in elderly patients with xerostomia.

Pilocarpine mouthwash relieved dry mouth in 19 elderly patients[26], whereas a systematic review evaluating the effectiveness of systemic pilocarpine in 242 elderly patients with xerostomia due to medication or unknown causes showed inconclusive results.[1] As our population is ageing and poly-pharmacy is common among elderly, more patients will be poly-medicated in the future. Hence, xerostomia will be a major problem and thus more research on this topic is necessary.

This study intends to deliver the “proof-of-concept” that locally administered pilocarpine drops are effective in reducing xerostomia complaints in a population of elderly (aged ≥ 70 years) with xerostomia at the expense of a minimum of side effects.

2. OBJECTIVES

Objective

This study intends to deliver the “proof-of-concept” that locally administered pilocarpine drops in two doses are effective in a population of elderly (aged ≥ 70 years) with xerostomia at the expense of limited adverse events. To this end, the study aims to quantify the effect size of pilocarpine in two different dosages. In case we observe clinically meaningful changes in xerostomia through measured NRS, a sufficiently-powered RCT will be prepared to compare pilocarpine to placebo.

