3. STUDY DESIGN

DESIGN:

Open-label randomised controlled pilot study

PARTICIPANTS

The study will be performed at the outpatient clinic internal medicine/elderly care of the Maastricht University Medical Centre+.

INTERVENTION:

The intervention concerns the treatment of xerostomia in 2 treatment groups:

1. low dose pilocarpine = 3 x 2.0 mg = 3 x 2 drops of pilocarpine 20.0 mg/ml (2%) per day
2. high dose pilocarpine = 3 x 5.0 mg = 3 x 5 drops of pilocarpine 20.0 mg/ml (2%) per day

The study lasts 21 days of which the first 14 days with medication and the last 7 days without medication to measure a possible “switch-on” effect.

MEASUREMENTS

Xerostomia	Numeric Rating Scale (NRS) Geriatric Oral Health Assessment Index (GOHAI-NL)
Concurrent symptoms	Utrecht symptom Diary (USD)
Generic Health-Related Quality of Life (HRQoL)	EuroQoL 5D (EQ5D)
Global Perceived Effect (GPE)	GPE 7-point scale
Side effects	4-point Likert scale (flu-like symptoms, sweating, headache, urinary frequency, diarrhoea, nausea, vomiting, palpitations, dizziness, rhinitis, other)
Whole resting saliva	Total amount of unstimulated saliva measured in 5minutes

Patient characteristics that are collected at inclusion include gender, age, primary diagnosis, co-morbidity, medication and relevant history.

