5. TREATMENT OF SUBJECTS

5.1 Investigational product/treatment

Patients will receive regular clinical care and pilocarpine drops in unit dose vials (Pilocarpine Minims (*nitraat*), eye drops, Bausch & Lomb), 2%, two or five drops administered three times a day (6 or 15mg/24h). Patients will receive the study drug for 14 days.

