10. STATISTICAL ANALYSIS

Primary and secondary study parameter(s)

Baseline characteristics will be described in detail per group in order to assess any imbalance. In case of missing data, we will use stochastic regression imputation to produce a synthetic part of the data to allow for an intention to treat analysis.

Per group, the post-treatment xerostomia score will be described as mean and standard deviation, or median and interquartile range in case of severe skewness. Additionally, we will compute a change-from-baseline score for both groups, which will be described in a similar matter. All secondary

outcome measures will be described in full using either mean and standard deviation or median and interquartile range for continuous measures, and count and proportion for categorical measures. For exploratory purposes, we will use the independent-samples t-test to test for differences in xerostomia complaint scores (NRS) between the two groups. However, as this is a pilot study, the emphasis will lie on clinical interpretation of the effect sizes of both groups separately. Preliminary analyses on secondary outcome measures will be performed using the independent samples t-test and Fisher's Exact test, depending on the measurement level of each variable.

Other study parameters

Not applicable.

Interim analysis

No interim analysis will be performed.

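### The stated aim is the effect size of pilocarpine at two doses, but with open-label pilocarpine in both arms the design identifies only an uncontrolled change per dose and an exploratory dose difference

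*Protocol*

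**What the plan says.** **Aim.** The Summary seeks proof of concept that "locally administered pilocarpine drops are effective in a population of elderly with xerostomia at expense of a minimum of side effects". Section 1 closes with the same intention, that "locally administered pilocarpine drops are effective in reducing xerostomia complaints in a population of elderly". Section 2 repeats it for two doses and says how it will be met: "To this end, the study aims to quantify the effect size of pilocarpine in two different dosages". The go step follows: "In case we observe clinically meaningful changes in xerostomia through measured NRS, a sufficiently-powered RCT will be prepared to compare pilocarpine to placebo".

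**Design.** Section 3 describes an "Open-label randomised controlled pilot study" with a low-dose and a high-dose pilocarpine group. Under Section 5.1, "Patients will receive regular clinical care and pilocarpine drops in unit dose vials", and this applies to both groups. Section 8.2 provides 24 envelopes, 12 for each dose. There is no placebo or untreated allocation.

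**Analysis.** Section 10 describes the post-treatment score and the change from baseline within each group. It then says: "For exploratory purposes, we will use the independent-samples t-test to test for differences in xerostomia complaint scores (NRS) between the two groups". It adds that "as this is a pilot study, the emphasis will lie on clinical interpretation of the effect sizes of both groups separately".

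**Use of the result.** Section 4.4 lists the effect size of pilocarpine among the unknowns and says the study will inform the sample size of a future trial.

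**Other measurements.** Under Section 8.3 the NRS is taken on days 0, 7, 14 and 21, and resting saliva is weighed on days 0 and 14. Medication stops after day 14.

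**The concern.** The effect of a drug at a dose is the difference between outcomes with it and without it. Here every participant takes pilocarpine, knows it, and rates their own dry mouth. Improvement within an arm may come from the drug, from expectation, or from anything else that changes over two weeks of ordinary care. The protocol nevertheless attributes the per-group result to pilocarpine and presents it as the means of showing that the drops work.

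Two things are at stake. The first is the pilot's own conclusion: followed as written, it would report as a drug effect a quantity that the design cannot separate from non-drug change. The second is what is carried into the next trial, since Section 4.4 promises sample-size input directly after naming the effect size as unknown.

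**Working it through.** The protocol has no power calculation to reproduce. Its sample size is 12 per group, 2 × 12 = 24, which agrees with the 24 envelopes in Section 8.2. The check is therefore about which quantities the design identifies.

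**Step 1. Write down what each arm shows.** Count improvement on the NRS as positive. For dose d, let P_d be the effect of pilocarpine against no pilocarpine, and N_d the change that would occur without any drug effect (expectation, natural course, concurrent care). The expected mean changes are:

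- low dose: C_L = P_L + N_L
- high dose: C_H = P_H + N_H

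**Step 2. Count the unknowns.** Make the favourable assumption that N_L = N_H = N, which randomisation supports except where knowing one's dose alters expectation. There are still three unknowns (P_L, P_H, N) and two observed means. Adding any constant to N and subtracting it from both P_L and P_H leaves the data unchanged. For example, if both arms were to improve by 2.0 points (an assumed figure), the data would fit P_L = P_H = 2.0 with N = 0, and equally P_L = P_H = 0 with N = 2.0.

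**Step 3. Look at the randomised contrast.** C_H − C_L = (P_H − P_L) + (N_H − N_L). Under the same assumption this is the dose difference P_H − P_L. Two equally effective doses give zero, and so do two ineffective ones. A non-zero difference would be informative about dose, but it does not give P_L or P_H.

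**Step 4. See whether the other measurements fill the gap.**

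- *Day 21, off drug.* Both arms stop together and openly. A return of symptoms would fit loss of drug effect or loss of expectation. Persistence would fit lasting non-drug change, or the lingering effect that Section 3 wants to look for. The rating is useful support but not a concurrent control.
- *Weighed saliva, days 0 and 14.* This is less exposed to expectation than a self-rating. It is still a before-and-after measure with everyone on drug, and it is a different outcome from the complaint score. Section 6.3 itself cites a trial in which flow rose without subjective benefit.

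**Step 5. Illustrate the caution about the next trial.** The protocol gives no inputs, so these are assumptions: an observed within-arm change of 2.0 points, SD 2.0 to 2.5, two-sided 5%, 80% power. Per arm, n = 2(1.960 + 0.842)² SD²/δ² = 15.7 SD²/δ².

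| Non-drug share of the 2.0 | True δ | n per arm needed (SD 2.0 to 2.5) | Power if sized on 2.0 |
|---|---|---|---|
| 0 | 2.0 | 16 to 25 | 81% |
| 0.5 | 1.5 | 28 to 44 | 56% |
| 1.0 | 1.0 | 63 to 99 | 29% |

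The last column applies to 16 per arm at SD 2.0 and 25 per arm at SD 2.5. For example, at SD 2.0 and δ = 1.5, the power is Φ(1.5/(2.0√(2/16)) − 1.960) = Φ(0.16) = 0.56. The table shows why the caution is worth stating. It does not predict this trial.

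**The case against.** The best defence is that the limitation is open and staged. The protocol calls itself an open-label pilot, treats the between-group test as exploratory, defers the placebo comparison to a powered trial, and defines the computed quantity in Section 10 plainly as a change from baseline. Meeting the go step leads only to preparing that trial, which could correct a wrong decision. Section 2 does not itself equate effect size with within-arm change; that reading comes from its go step together with Section 10. All of this stands and limits the harm. It does not correct an objective that still promises to show effectiveness by a route the design does not provide.

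Several stronger readings are tempting, and the documents do not support them:

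- *That the study yields nothing but uncontrolled change.* Section 10 also plans the randomised dose comparison.
- *That the pilot change will be the target difference of the placebo trial.* Section 4.4 does not say so. It sizes the study for precision about the mean and variance.
- *That the go step would often be met without a drug effect.* No threshold, SD or expected non-drug change is given, so no rate can be computed.
- *That regression to the mean inflates the change.* This matters only if the qualifying NRS serves as baseline. Section 11.2 puts day 0 at least 7 days after the invitation, so the day 0 rating may be separate.
- *That natural course or changes in co-medication explain much.* The entry criterion of more than 3 months of symptoms tempers the first. For the second, Section 1 regards withdrawing or replacing xerostomia-inducing drugs as the best remedy, and Section 8.3 does not reassess patient characteristics, which include medication, on day 14. But Section 1 also says such withdrawal is not always worthwhile, and a material shift within 14 days is speculative.

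**Conclusion.** The point holds and should be fixed. As written, the aim names a quantity, the effect of pilocarpine at each dose, that this design does not identify, and an efficacy conclusion drawn from it would be unsound. What the design does identify is an uncontrolled change per dose and an exploratory dose difference.

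This conclusion rests only on the allocation and the open-label design and needs no numerical assumption. The non-drug share of the change cannot be quantified from the protocol. The figures for a future trial depend wholly on the assumed SD and the assumed non-drug share. A missing placebo arm is not itself the fault: an uncontrolled pilot is a legitimate step if its result is named for what it is.

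**What to change.** 1. **Summary and Sections 1, 2 and 10.** Replace the statements that the drops are effective, the reference to pilocarpine's effect size and the reference to per-group effect sizes with *uncontrolled within-group change from baseline per dose*. Name the exploratory between-dose difference alongside it.
2. **Section 2, go step.** Word it as a decision to test pilocarpine against placebo, not as evidence of efficacy.
3. **Section 4.4, as a caution.** State that the within-arm change will not be taken as the drug-versus-placebo target difference of the future trial.

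The cost is protocol wording only, with no added patients, visits or measurements. The downside is a less favourable claim for the pilot, and the later trial will need a separately justified target difference.

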3. STUDY DESIGN

DESIGN:

Open-label randomised controlled pilot study

PARTICIPANTS

The study will be performed at the outpatient clinic internal medicine/elderly care of the Maastricht University Medical Centre+.

INTERVENTION:

The intervention concerns the treatment of xerostomia in 2 treatment groups:

1. low dose pilocarpine = 3 x 2.0 mg = 3 x 2 drops of pilocarpine 20.0 mg/ml (2%) per day
2. high dose pilocarpine = 3 x 5.0 mg = 3 x 5 drops of pilocarpine 20.0 mg/ml (2%) per day

The study lasts 21 days of which the first 14 days with medication and the last 7 days without medication to measure a possible “switch-on” effect.

MEASUREMENTS

Xerostomia	Numeric Rating Scale (NRS) Geriatric Oral Health Assessment Index (GOHAI-NL)
Concurrent symptoms	Utrecht symptom Diary (USD)
Generic Health-Related Quality of Life (HRQoL)	EuroQoL 5D (EQ5D)
Global Perceived Effect (GPE)	GPE 7-point scale
Side effects	4-point Likert scale (flu-like symptoms, sweating, headache, urinary frequency, diarrhoea, nausea, vomiting, palpitations, dizziness, rhinitis, other)
Whole resting saliva	Total amount of unstimulated saliva measured in 5minutes

Patient characteristics that are collected at inclusion include gender, age, primary diagnosis, co-morbidity, medication and relevant history.

4. STUDY POPULATION

4.1 Population (base)

The study will be performed at the outpatient clinic internal medicine/elderly care of the Maastricht University Medical Centre+ (MUMC+). Potentially eligible patients will be identified on the outpatient clinic and will be invited to participate when meeting the inclusion criteria.

4.2 Inclusion criteria

- ≥ 70 years of age
- Clinical diagnosis of chronic dry mouth defined as a Numeric Rating Scale (NRS) score ≥ 5 (scale 0 – 10, with 0 = no dry mouth and 10= worst possible dry mouth) on severity of xerostomia for more than 3 months.

4.3 Exclusion criteria

- Existence of cognitive impairment and/or diagnosis of dementia appraised by treating physician
- Inability to fill out the questionnaires due to other reasons
- Prior radiation therapy of the head-and-neck region

- Known m. Sjögren disease
- Contra-indications for parasympathomimetics (uncontrolled asthma, acute heart failure, active peptic ulceration, known hypersensitivity to pilocarpine, and when miosis is undesirable, e.g., in acute iritis and in narrow-angle (angle closure) glaucoma).

4.4 Sample size calculation

For this study we will take a pragmatic approach, as too little is known of the mean and variance of xerostomia complaints, quantified using the NRS, and the effect size of pilocarpine. This study will provide input for the sample size calculation for a future study. It would be feasible to include at least 24 patients in a period of 6 months, or 12 per group, as suggested as a rule of thumb for pilot studies to obtain sufficient precision about the mean and variance. [29]

5. TREATMENT OF SUBJECTS

5.1 Investigational product/treatment

Patients will receive regular clinical care and pilocarpine drops in unit dose vials (Pilocarpine Minims (*nitraat*), eye drops, Bausch & Lomb), 2%, two or five drops administered three times a day (6 or 15mg/24h). Patients will receive the study drug for 14 days.

5.2 Use of co-intervention (if applicable)

Not applicable

5.3 Escape medication (if applicable)

Not applicable

6. INVESTIGATIONAL PRODUCT

6.1 Name and description of investigational product(s)

Investigational product:

Pilocarpine Minims (*nitraat*), eye drops, Bausch & Lomb, 20 mg/ml (2%), 0.5 ml
(Oculoguttae pilocarpine sine conservans)

6.2 Summary of findings from non-clinical studies

We refer to the Summary of Product Characteristics (SmPC)

6.3 Summary of findings from clinical studies

Pilocarpine tablets are registered for dry mouth in Sjögrens disease and post radiation therapy.

Pilocarpine drops are registered for treatment of open-angle glaucoma and narrow-angle glaucoma and to antagonize mydriasis.

Pilocarpine tablets (systemic treatment) has proven to be effective in radiation-induced xerostomia,[15-18] Sjögrens disease, [19] tramadol induced oral dryness[20] and in patients taking xerogenic medications.[21] However, systemic administration of pilocarpine has frequent side-effects.

Off-label local oral administration of pilocarpine (drops, lozenges and mouthwashes) are reported to have none [24, 25] or minor local side effects (irritation of mouth and tongue).[26] In addition, a 5 mg pilocarpine lozenge produced better clinical results than a 5 mg pilocarpine tablet in 33 head-and-neck cancer patients.[27], Furthermore, pilocarpine eye drops 2% relieved xerostomia immediately in 19 patients with opioid-induced complaints of dry mouth.[25] However, inconclusive results have been reported about the effectiveness of these local formulations in other studies.[24, 28].

Dosing:

Post-radiation studies reveal an optimum oral dose of 5 mg 3 dd/day. Higher doses result in higher saliva flow but at the expense of more unacceptable adverse effects. Effect and side effects increase with increasing dosages.[15, 16] A trial with 2,5 mg 3dd/day showed an increase in salivary flow but not a subjective improvement.[18] Possibly this low dose is insufficient in damaged salivary glands. In this pilot study we will compare two doses (5 mg 3 dd/day and 2mg 3dd/day) in intact glands.

